Studies have shown that following primary vaccination with 13vPnC, circulating antibodies decline but are boosted following the booster dose after vaccination with the 12 – 15 month vaccination. This decline in circulating antibodies is not associated with increase in mucosal or invasive pneumococcal disease as antibodies are boosted in case of new colonization or infection with a vaccine-type *S. pneumoniae* after vaccinated with 13vPnC.^{18,19} Studies have also shown that one month after the booster dose, vaccinated children present an increase in B-memory-cells that return to baseline levels at the age of 24 months. The meaning of the boost effect on B-memory cells needs to be further elucidated but may be correlated with long term memory protection.^{20,21} As a part of Post Approval Commitments, the Center for Drug Evaluation (CDE) requested Pfizer to conduct an effectiveness study in a large scale population measuring herd protection in order to assess the clinical benefit; validate the correlation between surrogate endpoints (enzyme-linked immunosorbent assay [ELISA], MOPA) and protection, and the rationale of the criteria; investigate the immune persistence. This study is designed to assess the blood levels of circulating antibodies (IgG and MOPA) at the time of the diagnosis of clinical pneumonia.

Pfizer is currently conducting an observational study in Suzhou Children's Hospital (SCH) to evaluate 13vPnC vaccine effectiveness (VE) in preventing clinical pneumonia associated with 13vPnC vaccine type *S. pneumoniae* (study number WI232403). Pfizer will utilize the VE estimate from study WI232403 in combination with the post-approval commitment 3 (PAC3) immunogenicity study (study number B1851178) among infant cohort to estimate the correlation of protection (CoP). Additionally, based on recommendation from CDE, a descriptive immunogenicity study to measure the antibody levels at the time of disease onset was required. Therefore, this study will be conducted in parallel with the VE study in SCH to fulfill CDE request. Both the VE study (WI232403) and this immunogenicity sub-study, along with the analysis of CoP and the immune persistency portion included in study B1851178, will address these post licensure commitments from the CDE.

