5.2. Visit 1 (Enrollment)

1. Enroll the subject to this study, if eligible, and assign the participant to a study cohort.
2. Obtain and record the subject demography (including date of birth, sex, residence, and number/age of siblings, if any).
3. Obtain and record the subject's significant medical history (see [Section 6.1](#)).
4. For 13vPnC subjects, record date(s) of 13vPnC vaccination based on the patient's vaccine book.
5. Record antibiotic usage for the current pneumonia episode, to include antibiotic name, dosage, and start/stop date.
6. Collect a blood sample (approximately 5 mL) within 24 hours of enrollment. Blood must be drawn from peripheral veins (eg, arm, foot, or scalp veins). Drawing blood from central veins (eg, jugular or femoral veins), which may increase the risk associated with study participation, is not permitted.

7. Enter deep upper respiratory aspirate specimen information if this standard procedure was performed for this episode of pneumonia. The sample can be from before or after the enrollment. If an aspirate was not collected as a standard practice, this should be collected as a study procedure. The aspirate should be collected within 24 hours of enrollment.
8. Adverse events (AEs) that occur within 12 hours after the blood draw or aspirate collection (if collected as a study procedure) should be recorded in the source documents and in the AE section of the CRF.
9. The investigator or an authorized designee completes the CRF.

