6.1. Significant Medical History Collection

Significant medical malformation, any immunocomprised condition, spleen anomaly, bone marrow anomaly, and any other significant medical history at the discretion of the Investigator will be collected.

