8. DATA ANALYSIS/STATISTICAL METHODS

Detailed methodology for summary and statistical analyses of the data collected in this study will be documented in a Statistical Analysis Plan (SAP) and will be maintained by the sponsor.

The number and proportion of subjects with *S. pneumoniae* isolates detected will be summarized for both cohorts: the 13vPnC cohort and unvaccinated cohort. Additionally, the number and proportion of each serotype, serotype included in 13vPnC (VT), and serotypes not included in 13vPnC (non-VT) will be summarized for both cohorts.

For each cohort, children will be assigned to 2 groups: Participant in whom a 13vPnC vaccine type (VT) strain has been isolated from the respiratory tract, and participant from whom a 13vPnC VT strain has not been isolated from the respiratory tract (VT carrier versus without VT carrier). Therefore, a total of 4 subgroups are available: 13vPnC cohort with VT carrier; 13vPnC cohort without VT carrier; unvaccinated cohort with VT carrier; unvaccinated cohort without VT carrier.

For each of the 13 serotypes contained in 13vPnC, the IgG concentration and MOPA titers will be transformed in logarithm scale. Crude geometric mean concentrations (GMCs) and geometric mean titers (GMTs) and 95% confidence interval (CI) will be calculated for the 4 cohort/carriage subgroups.

A multiple regression model will be used with the log concentration or log titers as a dependent variable. Independent variables will include cohort (13vPnC or unvaccinated), 13vPnC VT carriage status, and the interaction of the cohort and carriage status, as well as the confounding variables (age at enrollment, residence location, season of enrollment). Adjusted GMCs (or GMTs) and adjusted geometric mean ratios (GMRs) along with 95% CI will be estimated based on this model. The (GMRs) will compare antibody levels between any 2 of the 4 subgroups, as well as between the 2 cohorts, and between the carriage status.

Additionally, serotype-specific GMC/GMT (or adjusted GMC/GMT) and 95% CI may be provided for each 13vPnC serotype carriage status (Yes/No), for both 13vPnC cohort and unvaccinated cohort. Similar to any 13vPnC VT carriage status, the descriptive comparisons will be presented as GMR (or adjusted GMR) and 95% CI.

All of the analyses are considered as descriptive and no multiplicity adjustment will be made.

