5.2.2. Analyses for Continuous Endpoints

For each of the 13 serotypes contained in 13vPnC Cohort and also Non-13vPnC Cohort, GMCs of IgG and GMT of MOPA will be calculated along with 2-sided 95% CIs, which will be constructed by back transformation of the CIs for the mean of the logarithmically transformed IgG/MOPA computed using Student's t distribution. In addition, the 2-sided 95% CI on the geometric mean ratios (GMRs) (the GMC of 13vPnC Cohort to the GMC of Non-13vPnC Cohort and the GMT of 13vPnC Cohort to the GMT of Non-13vPnC Cohort) for all 13 serotypes will be also provided and those 95% CIs will be constructed by back transformation of the CIs for the mean difference of the measures on the logarithmically transformed scale(IgG/MOPA) using Student's t distribution.

A multiple regression model will be used with the log concentration or log titers as a dependent variable. Independent variables will include cohort (13vPnC or unvaccinated), 13vPnC VT carriage status, and the interaction of the cohort and carriage status, as well as the confounding variables (age at enrollment, sex, season of enrollment). Adjusted GMCs (or GMTs) and adjusted geometric mean ratios (GMRs) along with 95% CI will be estimated based on this model. The (GMRs) will compare antibody levels between:

1. Within 13vPnC Cohort: VT-carrier + vs VT-carrier -
2. Within Non-13vPnC Cohort: VT-carrier + vs VT-carrier -
3. 13vPnC Cohort vs Non-13vPnC Cohort
4. Within VT-carrier +: 13vPnC Cohort vs Non-13vPnC Cohort
5. Within VT-carrier -: 13vPnC Cohort vs Non-13vPnC Cohort

Additionally, serotype-specific GMC/GMT (unadjusted) and associated 95% CI will be provided for each 13vPnC VT carriage status (Yes/No), for both 13vPnC cohort and unvaccinated cohort. GMRs (unadjusted) (GMC/GMT of VT- carrier + vs GMC/GMT of VT-carrier -) within 13vPnC Cohort and within unvaccinated Cohort, and GMRs (unadjusted) (GMC/GMT of 13vPnC Cohort vs GMC/GMT of Non-13vPnC Cohort) within

VT-carrier + group and within VT-carrier group and associated 95% CIs will be calculated using Student's t distribution for the mean difference of the measures on the logarithmically transformed scale (IgG/MOPA).

If model adjusted GMCs, GMTs, GMRs are not estimatable (e.g., due to limited data), then only unadjusted GMCs, GMTs, GMRs and associated 95% CIs will be presented.

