6.2. Baseline and Other Summaries and Analyses

6.2.1. Baseline Summaries

Subjects demographics (collected information including, sex, residence, and number of siblings, if any) and medical history will be descriptively summarized.

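### The adjusted antibody ratios leave out siblings, a household-exposure measure that the study already records; this is a possible confounder of modest, unquantified size

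*SAP*

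**What the plan says.** - **Adjusted model.** SAP section 5.2.2 regresses log IgG or log MOPA titer on cohort, vaccine-type (VT) carriage and their interaction, plus "confounding variables (age at enrollment, sex, season of enrollment". Five GMRs follow: carriers against non-carriers within each cohort (1, 2), cohort against cohort (3), and cohort against cohort within each carriage stratum (4, 5).
- **Protocol version of the model.** Protocol section 8 lists "confounding variables (age at enrollment, residence location, season of enrollment". The SAP has sex where the protocol has residence and gives no reason. Neither list contains siblings or medical history.
- **Sibling data.** Protocol section 5.2 instructs the site: "Obtain and record the subject demography (including date of birth, sex, residence, and number/age of siblings, if any". SAP section 6.2.1 uses this only in a baseline table and names the number of siblings, not their ages: "Subjects demographics (collected information including, sex, residence, and number of siblings, if any) and medical history will be descriptively summarized".
- **Medical history.** Protocol section 6.1 collects "any immunocomprised condition, spleen anomaly, bone marrow anomaly". Exclusion 2 in protocol section 4.2 lets the investigator turn away a child whose condition could interfere with interpretation.
- **Matching.** Under protocol section 5, controls share the vaccinated child's age band and are admitted within 7 days either way.
- **Primary and sensitivity analyses.** SAP section 6.1.1 makes the crude geometric means in the four cohort-by-carriage subgroups primary. SAP section 6.1.2 plans no sensitivity analysis.

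**The concern.** The SAP itself labels its covariates as confounders, so the adjusted ratios are meant to be read with confounding reduced. Household exposure is an obvious candidate. Carriage status comes from culture of an aspirate taken for one pneumonia episode. A child exposed at home is more likely to carry at that moment. The same child may also hold antibody from an earlier colonization that has since cleared, which the carriage variable does not capture. For children already vaccinated, the protocol's introduction supports part of this: "antibodies are boosted in case of new colonization or infection with a vaccine-type" strain. For unvaccinated children the same mechanism is an assumption.

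If it operates, comparisons 1 and 2 would show a carriage difference that partly reflects family size. Comparisons 3 to 5 would shift if vaccinated and unvaccinated children come from families of different size. Matching on age band and date does not balance family size, and it has no bearing on contrasts within a cohort. The data needed to adjust are already on the case report form.

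**Working it through.** **Step 1. Group sizes (protocol section 3.3).** 3,800 × 2 years × 0.05 = 380, as stated. 380 × 0.30 = 114, which the protocol gives as about 100. With the 1:2 ratio, 100 + 200 = 300, as stated. IgG is therefore about 100 against 200. MOPA is about 100 against 100, because SAP section 3.1 limits the unvaccinated sample to the number of vaccinated children tested.

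**Step 2. Assumed inputs.** The documents give none of these.
- Having a sibling multiplies IgG by k = 1.2, 1.5 or 2.0.
- 50% of unvaccinated and 35% of vaccinated children have a sibling.
- VT carriage is 15% without a sibling; the odds ratio for carriage with a sibling is 1.5 to 2.5.
- The SD of log10 antibody is 0.4 to 0.6.

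**Step 3. Bias from omitting a binary covariate.** Bias factor = k^d, where d is the difference in sibling share between the groups compared.

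Unvaccinated carriers against non-carriers, with no true carriage effect:
- Odds ratio 1.5: carriage with a sibling is 0.209. Sibling share is 0.583 in carriers and 0.482 in non-carriers, so d = 0.10.
- Odds ratio 2.5: carriage with a sibling is 0.306. Shares are 0.671 and 0.449, so d = 0.22.

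Vaccinated against unvaccinated: d = 0.35 − 0.50 = −0.15.

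| k | Carriage GMR, unvaccinated (null = 1) | Multiplier on cohort GMR |
|---|---|---|
| 1.2 | 1.02 to 1.04 | 0.97 |
| 1.5 | 1.04 to 1.09 | 0.94 |
| 2.0 | 1.07 to 1.17 | 0.90 |

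A wider grid, k from 1.25 to 2.0 and d from 5 to 30 points, gives 1.01 to 1.23.

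**Step 4. Sampling error for comparison.** 95% CI factor = 10^(1.96 × SD × √(1/n₁ + 1/n₂)).
- Cohort GMR, IgG, 100 against 200: 1.25 to 1.39.
- Cohort GMR, MOPA, 100 against 100: 1.29 to 1.47.
- Unvaccinated carriage GMR, IgG: the step 2 inputs imply overall carriage of (0.15 + 0.209)/2 = 0.18 to (0.15 + 0.306)/2 = 0.23, or about 36 to 46 carriers in 200. The factor is 1.39 to 1.65 with 36 carriers and 1.35 to 1.58 with 46.
- Vaccinated carriage GMR, with an assumed 5 to 20 carriers in 100: 1.57 to 3.46.

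The largest biases in the table, 1.17 for carriage and 1/0.90 = 1.11 for cohort, lie below the smallest matching CI factors, 1.35 and 1.25.

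**Step 5. Immune, spleen and bone-marrow history.** If such a condition multiplies antibody by 0.25 to 0.5 and its prevalence differs by 1 to 5 points (both assumed), the bias factor is 0.93 to 0.99. In a subgroup of 10, one child with 10-fold lower IgG multiplies the geometric mean by 10^(−1/10) = 0.79, and one with 3-fold lower IgG by 3^(−1/10) = 0.90. The CI factor for a geometric mean of 10 children is 10^(2.262 × SD/√10) = 1.93 to 2.69, so both shifts lie well inside it.

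**Step 6. Degrees of freedom.** With age linear and season in four categories (assumed), the model has 9 coefficients: intercept, cohort, carriage, interaction, age, sex and three for season. That leaves 300 − 9 = 291 for IgG and 200 − 9 = 191 for MOPA.

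**The case against.** The study is declared descriptive, and its primary analysis is a set of crude subgroup means. The adjusted ratios are supporting results, and covariate choice in a supporting model is partly a matter of preference. No passage links siblings to vaccination, carriage or antibody. Every input to the bias calculation is assumed, and the upper end needs a sibling both to double IgG and to carry an odds ratio of 2.5. Even then the shift is within sampling error.

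Most of this stands as a limit on size. It does not remove the point. A descriptive label does away with hypothesis tests, not with confounding, and the SAP chose to report ratios adjusted for confounders. A shift of this kind also does not average out, and it could push a contrast the same way across serotypes.

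Two stronger readings are tempting and not supported:
- A reader might infer that the protocol establishes antibody boosting by colonization in all children. The sentence in its introduction is restricted to children already vaccinated, so it does not carry the argument for the unvaccinated cohort.
- A reader might infer that immune, spleen and bone-marrow history is an equally serious omission, because vaccinated VT carriers would tend to be poor responders. No passage says so. Exclusion 2 partly handles such children, though at the investigator's discretion, and low antibody at diagnosis is part of what the study sets out to describe.

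**Conclusion.** The omission is real: sibling data are collected, enter neither adjusted model, and are otherwise only tabulated by number. Siblings are a possible, unquantified confounder of comparisons 1 to 5. The documents do not show that bias is present. Under the step 2 assumptions the effect is modest, about 1.02 to 1.17 on the unvaccinated carriage ratio and about 0.90 to 0.97 on the cohort ratio, and generally smaller than sampling error. It is least visible in the vaccinated carriage ratio, where carriers may be few. The crude primary means are unaffected. The case for acting rests on the very low cost and on fixing the covariate before results are seen. The immune-history issue is minor: such children are probably few (an assumption), and the average effect is about 1% to 7%.

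**What to change.** - **Main change, SAP section 5.2.2.** Add one prespecified sibling term to the adjusted model for all 13 serotypes and both assays: either any sibling under 5 years (yes/no) or number of siblings (0, 1, 2 or more). Reporting it as a prespecified supplementary adjusted model would also do.
- **Cost.** SAP wording and 1 to 2 degrees of freedom, out of about 290 for IgG and about 190 for MOPA. No new data are needed. Children with missing sibling data drop out of the adjusted model, so their number should be reported. The existing fallback to unadjusted results when the model cannot be estimated still applies.
- **Optional, lower priority, SAP section 6.1.2.** Repeat the four-subgroup table once without children who have a recorded immunocompromising, spleen or bone-marrow condition, and give the number excluded per subgroup. Expect little change. This suits rare conditions better than a sparse covariate.

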5.3. Methods to Manage Missing Data

In general, nonmissing values will not be excluded from the analysis. However, certain statistical procedures that compare 2 or more variables, or values at more than 1 time point, for the same subject require all values to be available. In such cases, nonmissing values will be dropped to the extent necessary to perform the procedure.

5.3.1. Immunogenicity Data

Immunogenicity data collected for this study are the results of immunologic assays performed by the National Institutes for Food and Drug Control (NIFDC) on the blood samples collected.

The Lower Limit of Quantitation (LLOQ) in micrograms per mL ($\mu\text{g/mL}$) for each serotype is shown in Table 2.

Table 2. The LLOQ in Micrograms per mL from NIFDC

Serotype	LLOQ
1	0.02
3	0.03
4	0.02
5	0.03
6A	0.03
6B	0.03
7F	0.04
9V	0.02
14	0.04
18C	0.02
19A	0.02
19F	0.03
23F	0.03

Antibody concentrations above LLOQ are considered accurate and their quantitated values will be reported. The Limit of detection (LOD) was established as 50% of the LLOQ. Values below the LLOQ or denoted Below Limit of Quantification (BLQ) will be set to **0.5 \times LOD** for analysis.

The NIFDC's OPA LLOQ in titers for all serotypes was set as 8. For the results of antibody titers that are below the LLOQ, or denoted as BLQ, $0.5 \times \text{LLOQ}$ will be assigned for analysis.

No other missing assay data will be imputed in the analyses. All immunogenicity analyses will be performed after the imputation of the antibody concentrations or antibody titers that are below the LLOQ.

For each serotype's antibody concentrations or antibody titers, the number of subjects with missing values at each blood sampling point will be provided.

5.3.2. Safety Data

Handling of missing information related to safety data, such as missing or partially missing date, will be in accordance with Pfizer reporting standards.

6. ANALYSES AND SUMMARIES

All summaries will be applied to evaluable population. Any subjects that are enrolled but did not meet study inclusion/exclusion criteria will be listed.

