4. ANALYSIS SETS (POPULATIONS FOR ANALYSIS)

Population	Description
Enrolled	All participants who signed the informed consent document.
Evaluable	All participants who signed the informed consent document, met all inclusion/exclusion criteria, and had at least one immunogenicity assay value available for analysis.

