5.2. General Methods

5.2.1. Analyses for Binary Endpoints

For carriage results, the exact 2-sided 95% confidence intervals (CIs) (Clopper-Pearson CIs) will be provided for the proportions of subjects with VT or serotype-specific carriage.

The exact CIs (Clopper-Pearson) for the various proportions of individual groups will be computed using the F distribution. If r is the number of responses and n is the number of subjects, then it follows that $p=r/n$ is the estimate of the proportion of responses. An exact 95% CI can be computed by solving the following 2 equations. For the lower limit P_L ,

$$p_L = \frac{rF_L}{(rF_L + (n - r + 1))}$$

and for the upper limit P_U ,

$$p_U = \frac{(r+1)F_U}{(n-r)+(r+1)F_U}$$

where F_L is the quantile from the F distribution for $\alpha=0.025$, with numerator degrees of freedom equal to $2r$ and denominator degrees of freedom equal to $2(n-r+1)$. F_U is the quantile from the F distribution for $\alpha=0.975$, with numerator degrees of freedom equal to $2(r+1)$ and denominator degrees of freedom equal to $2(n-r)$. When r equals 0, F_L should be set equal to 1.0 so P_L equals 0. When r equals n , F_U should be set equal to 1.0 so P_U equals 1.0.

The CI using the F distribution is described in Collett (1991)¹ and implemented in SAS PROC FREQ.

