6.2.2. Deep Upper Respiratory Aspirates Culture Summaries

The number and proportion of subjects with *S. pneumoniae* isolates detected will be summarized for both cohorts: the 13vPnC cohort and unvaccinated cohort. Additionally, the number and proportion of each serotype, serotype included in 13vPnC (VT), and serotypes not included in 13vPnC (non-VT) will be summarized for both cohorts.

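### The SAP computes culture, serotype and carriage proportions only in children with an antibody result, so valid cultures from other eligible children are left out of every planned output; the effect is probably small.

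*SAP*

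**What the plan says.** SAP section 4 defines two sets. Enrolled is "All participants who signed the informed consent document". Evaluable adds two conditions: the child "met all inclusion/exclusion criteria, and had at least one immunogenicity assay value available for analysis".

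SAP section 6 then sets one rule for all output: "All summaries will be applied to evaluable population". It promises one listing outside that set: "Any subjects that are enrolled but did not meet study inclusion/exclusion criteria will be listed". No summary is assigned to the Enrolled set.

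Two parts of the SAP deal with culture results:

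- SAP 6.2.2: "The number and proportion of subjects with *S. pneumoniae* isolates detected will be summarized for both cohorts: the 13vPnC cohort and unvaccinated cohort". Counts and proportions by serotype, and by VT and non-VT, follow.
- SAP 5.2.1: exact (Clopper-Pearson) 95% intervals "will be provided for the proportions of subjects with VT or serotype-specific carriage".

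Neither names a population, so the section 6 rule governs both. Protocol section 8 plans the same culture summaries by cohort. It sets no antibody condition, but it names no analysis population either.

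**The concern.** A carriage proportion uses the aspirate, not the serum. The two samples are collected separately: under protocol sections 3 and 6.2.2 the aspirate normally comes from standard care, possibly before enrollment, and is otherwise taken as a study procedure. A failed or unusable blood draw does not make a culture invalid. Under the SAP as written, however, the child leaves both numerator and denominator.

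This sits badly with SAP 5.3, which in general keeps nonmissing values and drops them only where a procedure needs several variables from the same child. A carriage proportion is not such a procedure.

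A missing assay value is foreseeable. Children are enrolled from 5 months of age, about 5 mL is sought, and only peripheral veins may be used (protocol 5.2). Protocol section 6 expects that some tests cannot be done, and SAP 5.3.1 plans to count missing assay values.

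At stake are the precision of a descriptive table and, if children without serum differ in carriage, its point estimates.

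**Working it through.** **1. Does another planned output show the omitted cultures?**

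- Section 6 listing: covers only children who failed inclusion/exclusion criteria, so not an eligible child without serum.
- SAP 5.3.1: counts missing assay values per serotype, with no culture result.
- SAP 6.2.3: lists adverse events only.
- SAP 6.1.2: plans no sensitivity or supplementary analysis.

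None does.

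**2. Who would lack every assay value?**

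Protocol 6.2.2.1.1 plans ELISA for all children with a blood sample. One value is enough for the Evaluable set, so not being chosen for the MOPA subset removes nobody. Results below the LLOQ are given an assigned value (SAP 5.3.1), so low antibody removes nobody either. What remains is children with no usable serum.

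**3. The plan's own cohort sizes (protocol 3.3)**

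- Eligible for the vaccinated cohort: 3,800 × 2 × 0.05 = 380, as stated.
- Consented: 380 × 0.30 = 114, which the protocol rounds down to about 100.
- Total: 100 + 2 × 100 = 300, as stated.

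I use 100 vaccinated children. The point does not depend on the rounding.

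**4. Size of the effect**

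Assumptions, since the documents give no figures: N = 100 with r = 20 carriers, and d children without an assay value, of whom c are carriers. The SAP would report (r − c)/(N − d). Intervals are Clopper-Pearson 95%.

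Nobody missing: 20/100 = 20.0% (12.7 to 29.2).

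| d | c = d (all are carriers) | c = 0 (none are) |
|---|---|---|
| 2 | 18/98 = 18.4% | 20/98 = 20.4% |
| 5 | 15/95 = 15.8% | 20/95 = 21.1% |
| 10 | 10/90 = 11.1% | 20/90 = 22.2% |

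These are outer bounds. Less extreme cases:

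- d = 5, c = 1 (same carriage rate): 19/95 = 20.0% (12.5 to 29.5).
- d = 5, c = 2 (twice the rate): 18/95 = 18.9% (11.6 to 28.3).
- d = 10, c = 2 (same rate): 18/90 = 20.0% (12.3 to 29.8).
- d = 10, c = 4 (twice the rate): 16/90 = 17.8% (10.5 to 27.3).

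With d = 5, the bounds are 5.3% to 10.5% if assumed carriage is 10% (5/95 and 10/95), and 26.3% to 31.6% if it is 30% (25/95 and 30/95).

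**The case against.** The strongest defence is that the restriction is deliberate and coherent. The study's only objective is antibody level by vaccination and carriage status. Carriage is a classifier, and the culture table sits among the baseline and other summaries. Describing the same children whose antibodies are analysed makes that table match the four antibody subgroups. The group left out should also be very small: blood is taken from all participants, a contraindicated draw is an exclusion criterion, and one ELISA value is enough. Nothing in the documents shows that failed draws are related to carriage, and the doubled-rate shifts above lie well inside the full-cohort interval.

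Most of this stands and limits the point to a minor one. The wish for matching denominators is met by printing both. It does not explain why a valid culture should be left out of a table that needs no serum.

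A reader might infer more than the documents support:

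- *That the SAP contradicts the protocol.* Protocol section 8 names no population for any summary and leaves detail to the SAP. Its silence on an antibody condition is not a contrary rule.
- *That these children or their isolates vanish.* A child could still appear in the adverse event listing or the missing-value count, and isolates are serotyped within study WI232403. The supported statement is narrower: no output planned in this SAP shows their culture results.
- *That half of the unvaccinated cohort would be dropped.* Footnote d of the protocol's Schedule of Activities can be read as limiting ELISA as well as MOPA to a subset of unvaccinated children. At an assumed 20% carriage, going from 200 to 100 children would widen the interval from 14.7–26.2% to 12.7–29.2%. But protocol 6.2.2.1.1 gives ELISA to every child with a blood sample, and protocol 6.2.2.1.2 and SAP 3.1 describe the subset for MOPA only. The footnote should be reconciled with them, but it does not establish the larger loss.

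**Conclusion.** The point holds as a minor one. As written, the SAP leaves valid cultures from eligible children without an assay value out of the culture, serotype and carriage proportions, against the general rule in its own section 5.3.

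The effect is zero if every child has an assay value and is probably small otherwise. Under the assumed 20 carriers in 100 with five children missing, the reported figure lies between 15.8% and 21.1%. If missingness is unrelated to carriage, the estimate is not biased and the interval widens slightly, from 12.7–29.2% to 12.5–29.5%. The direction and actual size cannot be determined, because the documents give no missing-serum or carriage rate. The antibody analyses are unaffected, and the Evaluable set is right for them.

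**What to change.** Replace the population sentence in SAP section 6 with:

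> Antibody summaries use the Evaluable population. Culture and serotype summaries (5.2.1, 6.2.2) use all enrolled children who met inclusion/exclusion criteria and have an aspirate culture result, with the Evaluable subset shown beside it.

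The four cohort-by-carriage antibody subgroups stay in the Evaluable set. The cost is a short text change and one extra column, with no new data collection. The downside is that the carriage table may have a slightly larger n than the antibody tables, which the extra column explains.
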